1.4 Study Rationale and Risk Analysis (Risks to Benefits Ratio)

1.4.1 Study Rationale

We hope to further characterize and define the role of consumer-facing technology in the clinical environment by focusing on device accuracy when compared to standard clinical monitoring in patients undergoing an endoscopic procedure. We will generate and answer questions related to these devices that have not yet been explored in the gastroenterology literature. We will provide a timely and much-needed framework that addresses both practical and theoretical considerations around a technology that has become increasingly relevant to patients.

This study will specifically address whether consumer facing wearable devices can serve as patient monitoring devices in a comparable manner to the current gold standard in the procedural suite. In addition to accuracy, we will assess whether certain procedural maneuvers interfere with device data collection. This information will be relevant to patients, providers and healthcare institutions and can help inform policy regarding these devices.

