3.1 General Design

We will perform a prospective, non-blinded, exploratory study to assess the accuracy and safety of smart technology in the endoscopy suite for patients undergoing gastrointestinal endoscopic procedures with sedation. We will also simultaneously perform an assessment of patient and provider preferences using narrative-driven, qualitative evaluation.

Patients will be identified by reviewing daily procedure listings on endoscopy units on Alfred 6, Gonda 2 and Gonda 9. Recruitment will occur over the phone the day prior to a procedure, or the pre-procedure areas on the day of the procedure. Patients who meet inclusion criteria and consent to participation in the study will be provided the smart devices. The devices will be secured to the wrist and torso by study personnel prior to administration of sedatives. The smart watch will be programmed to record respiratory rate, heart rate, and oximetry using native, first party device applications. These applications include *Blood Oxygen* (measures oxygen saturation), *ECG* (records single lead ECG), *Heart Rate* (heart rate), and *Health* (which logs respiratory rate while sleeping). The QardioCore ECG device will measure a single-lead ECG, heart rate, skin temperature, and respiratory rate.

The patient will undergo his or her scheduled procedure. Patients, proceduralists and anesthetists will not be blinded to their enrollment as the devices will be visible. On completion of the procedure, the devices will be removed by the study coordinator and data downloaded onto a central device for analysis. Procedural information will be extracted from the operative note, sedation record, and anesthesia encounter in EPIC. The day after the patient's procedure, a survey will be submitted to them electronically which will remain open until 14 days after

the procedure. Aen electronic reminder will be sent if uncompleted at 7 days, followed by a telephone reminder if not completed at 13 days. There will be no additional patient follow up after completion of the survey. At study completion, a survey will be sent to involved proceduralists and anesthetists.

3.2

Figure 1: Study Design

[figure not shown]

Table 1. Schedule of Events

	Baseline Screening & Enrollment Visit 1 Days -60 to 0	Accrual: Study Intervention Visit 2 Day 0	Patient Survey Visit 3 Day +1 to +14	Provider survey Days 0 to 180
Inclusion/ Exclusion	X	X (if not performed earlier)		
Device(s) Placement/ Recording		X		
Patient Survey			X	

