4.4 Early Withdrawal of Subjects

4.4.1 When and how to Withdraw Subjects

The subjects will undergo the clinically indicated procedure with the wearable devices. Early withdrawal would include removal of the devices prior to procedure completion, which can be performed at the discretion of the patient or clinical providers at any point.

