4.4.2 Data Collection and Follow-up for Withdrawn Subjects

Withdrawn subjects will be recorded in the study record in order to calculate the withdrawal rate. There will be no further utilization of any subject related data.

5 Statistical Plan

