5.1 Sample Size Determination

Power analysis not performed as this study is descriptive and we do not plan to perform any statistical testing.

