5.2 Statistical Methods

Descriptive Statistics

Baseline values for demographic, clinical, and outcome will be tabulated for the study subjects. Continuous variables will be expressed as mean and standard deviation. Categorical variables will be expressed as percentages.

We will measure the rate of concordance between device detection and documentation in anesthesia record (# of events recorded on wearable device / events noted on anesthesia record). Events to be recorded include tachycardia (HR > 100), bradycardia (HR < 60), desaturation (peripheral O₂ saturation < 88%), any arrhythmia, and tachypnea (RR > 18).

We will also calculate the difference in maximum and minimum heart rate, respiratory rate, and oxygen saturation recorded by the watch compared to the sedation record.

Handling of Missing Data

Subjects with missing or incomplete data will be noted but will not include in the final analysis. Available information regarding these patients will be reported separately to allow for evaluation of external validity

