5.3 Subject Population(s) for Analysis

All subjects who wore the device for the duration of procedure will be included in the analysis.

6 Safety and Adverse Events

Patients will be undergoing endoscopic procedures that are clinically indicated with inherent risk of the procedure itself. There will be minimal additional risk with placement of a smart device in the pre-operative area. Wearable technologies (eg. smartphones, smart watches) are already permitted in the endoscopy suite, so this protocol would not significantly alter standard of care. Therefore, this study will not track any adverse events.

Definitions

Adverse Effect (Event)

Any untoward medical occurrence in a subject involved in clinical study of an investigational device; regardless of the causal relationship of the problem with the device or, if applicable, other study related treatment(s).

Life-threatening adverse effect: Any adverse effect that places the subject, in the view of either the investigator or the sponsor, at immediate risk of death from the effect **as it occurred**. It does not include a reaction that, had it occurred in a more severe form, might have caused death.

Serious adverse effect: An adverse effect is considered “serious” if, in the view of either the investigator or the sponsor, it results in any of the following outcomes:

- death
- a life-threatening AE
- inpatient hospitalization or prolongation of existing hospitalization
- a persistent or significant disability/incapacity
- a congenital anomaly/birth defect.

Unanticipated adverse effect: Any adverse effect, the nature, specificity, severity, or frequency of which is not consistent with the risk information in the clinical study protocol or elsewhere in the current IDE application.

All inclusion and exclusion criteria are set out and there will be no protocol deviation.

7 Data Handling and Record Keeping

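### The plan says it will assess whether procedural maneuvers interfere with device recording, but it specifies no analysis by maneuver, and its missing-data rule takes interrupted recordings out of the final analysis

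*Combined protocol and SAP*

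**What the plan says.** The study rationale (section 1.4.1) states that, beyond accuracy, "we will assess whether certain procedural maneuvers interfere with device data collection", and presents the result as something that can inform policy. The listed objectives in sections 2.1 and 2.2 do not include interference.

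The relevant data source is in section 3.1: "Procedural information will be extracted from the operative note, sedation record, and anesthesia encounter in EPIC". It gives no list of maneuvers and no timing.

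Four statements decide whose data are analysed:

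- Section 5.2, on missing data: "Subjects with missing or incomplete data will be noted but will not include in the final analysis".
- Section 5.2, next sentence: "Available information regarding these patients will be reported separately to allow for evaluation of external validity".
- Section 5.3: "All subjects who wore the device for the duration of procedure will be included in the analysis".
- Section 4.4.1: "Early withdrawal would include removal of the devices prior to procedure completion", at the discretion of the patient or the clinical providers. For withdrawn subjects, section 4.4.2 says: "There will be no further utilization of any subject related data", apart from counting them for the withdrawal rate.

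The planned accuracy measures in section 5.2 are an event concordance rate and differences in maximum and minimum vital signs. Neither is broken down by maneuver. Section 5.1 says: "Power analysis not performed as this study is descriptive and we do not plan to perform any statistical testing".

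**The concern.** The most direct sign that a maneuver interferes with data collection is a gap or a failed recording. Section 5.2 makes complete data a condition of entry to the final analysis, so that analysis is selected on the outcome of the interference question. Among the subjects kept, data loss is nil with and without a maneuver, whatever the truth.

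Two things are at stake. A question that the protocol says it will address has no planned answer. The primary objective is also affected: if poor signal produces both gaps and inaccurate readings, dropping interrupted recordings makes the devices look more accurate than they would be in routine use. That matters for a study meant to inform institutional policy on these devices.

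**Working it through.** The plan has no power, precision or failure-rate figure to reproduce; 500 is a recruitment target (section 4). The check has two parts.

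**1. What happens to each kind of subject**

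| Subject | 5.2 | 5.3 | 4.4.1–4.4.2 |
|---|---|---|---|
| Wore device throughout, complete data | in final analysis | in analysis | not applicable |
| Wore device throughout, recording gap | out; noted and reported separately, if the gap counts as incomplete | in analysis | not applicable |
| Device removed early, by patient or provider | out if the data count as incomplete | out | withdrawn; counted only, data not used |

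The second row is a direct conflict between 5.2 and 5.3, and it concerns the subjects who carry the information on data loss. In the third row, a device taken off because it was in the way of a maneuver would be relevant to the question, yet its data may not be used. No section tabulates any of these groups by maneuver.

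**2. Illustrative size, on assumed rates**

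Inputs: N = 500 (section 4). The following are assumed, because the protocol gives none of them: share exposed to a maneuver, s = 20%, 40% or 60%; recording failure with the maneuver (p1) and without it (p0) of 10% v 5%, 20% v 5% or 30% v 10%. Every recording failure is taken to trigger the 5.2 exclusion.

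- Excluded = N·s·p1 + N·(1−s)·p0.
- Difference in failure if excluded subjects are counted as outcomes = p1 − p0.
- 95% half-width = 1.96·√[p1(1−p1)/(N·s) + p0(1−p0)/(N·(1−s))].

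Worked case, s = 40%, 20% v 5%: excluded = 200×0.20 + 300×0.05 = 40 + 15 = 55, leaving 445. Half-width = 1.96·√(0.16/200 + 0.0475/300) = 0.061.

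| s | p1 v p0 | Excluded (of 500) | True difference (points) | Half-width (points) |
|---|---|---|---|---|
| 20% | 10 v 5% | 30 | 5 | 6.3 |
| 20% | 20 v 5% | 40 | 15 | 8.1 |
| 20% | 30 v 10% | 70 | 20 | 9.5 |
| 40% | 10 v 5% | 35 | 5 | 4.8 |
| 40% | 20 v 5% | 55 | 15 | 6.1 |
| 40% | 30 v 10% | 90 | 20 | 7.2 |
| 60% | 10 v 5% | 40 | 5 | 4.5 |
| 60% | 20 v 5% | 70 | 15 | 5.4 |
| 60% | 30 v 10% | 110 | 20 | 6.6 |

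Exclusions run from 30/500 = 6% to 110/500 = 22%. In every row the difference within the retained set is 0, by construction and not as evidence about these devices. Counting the excluded subjects as outcomes recovers differences of 15 to 20 points clearly. A 5-point difference would be estimated only roughly.

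**The case against.** A reader might infer that affected subjects are deleted and that the question cannot be answered. The documents do not support this. The sentence after the exclusion rule keeps these subjects visible through separate reporting, and section 3.1 supplies procedural information by which they could be grouped. Section 5.3, read alone, keeps anyone who wore the device throughout, gap or no gap. Only subjects whose device came off early are barred from use. That part of the objection stands.

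Further points in the plan's favour also stand:

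- The protocol undertakes to assess interference, not to test a hypothesis, and section 5.1 rules out testing. Interference appears in the rationale and not among the objectives.
- Interference need not mean a gap. Readings that are complete but wrong would stay in the final analysis and could affect the maximum and minimum differences or the event concordance.
- Section 5.2 does not define incomplete data, so a brief gap might not trigger exclusion.
- Dropping the exclusion rule would not by itself supply the missing maneuver list, timing, outcome definition or comparison. Lack of specification is the more basic gap.

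These points narrow the concern but do not remove it. Separate reporting is for external validity, and no section plans to set it against maneuvers. No breakdown by maneuver is planned for wrong-but-complete readings either. The conflict between 5.2 and 5.3 leaves the analyst without a rule for a subject with a gap.

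**Conclusion.** The concern holds in a limited form. The protocol undertakes to assess interference and specifies no analysis for it. Under section 5.2, the final analysis set cannot show interference that takes the form of lost recording, and the accuracy results are selected toward good recordings. The data to be collected could address the question; the planned analysis does not. Sections 5.2 and 5.3 disagree on subjects with gaps, and section 4.4.2 bars use of data after early removal.

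The selection follows from the rule and does not depend on any assumed rate, provided a gap or failure counts as incomplete data. Its size does depend on assumptions: about 6–22% of 500 subjects excluded over the range shown. The documents allow no estimate of how far the accuracy figures would shift. Because interference is not a listed objective and the affected subjects are still reported, this should be corrected before analysis but does not undermine the study as a whole.

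**What to change.** In section 5.2:

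- Exempt device-side gaps and failures from the exclusion. Count them as an outcome, for example any recording failure or the share of the procedure with device data, in all subjects who had a device placed. Define the outcome separately for the wrist and torso devices. The share needs an expected recording frequency for each measure, which the protocol does not give; any recording failure is the simpler choice, once failure is defined.
- Name the maneuvers of interest and code them from the operative note already being extracted, with clock times where they exist.
- Report the outcome overall and by maneuver as proportions or means with 95% confidence intervals. This is descriptive and consistent with section 5.1.
- Keep subjects with partial device data in the accuracy analysis for the measures they have.

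Report early device removals by reason, as far as consent allows, and reconcile sections 4.4.2, 5.2 and 5.3 so that one rule applies to each kind of subject.

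The cost is a little more chart abstraction and analysis, with no extra visits. Device performance will probably look less favourable once failures are counted.

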1.4.2 Anticipated Risks

Patients would be undergoing endoscopic procedure that was clinically indicated with inherent risk of the procedure but minimal additional risk with placement of a watch in the pre-operative area. Wearable technologies (e.g. smartphones, smart watches) are already permitted in the endoscopy suite, so this protocol would not significantly alter standard of care.

There is a minimal risk of allergic reaction to a component of the watch or band. The devices may be re-used for multiple procedures or handled by study personnel and therefore carries the risk of transmitting infection. Precautions will be taken to ensure that all devices are cleaned similarly to reusable devices in the procedural suite. As with all research, there is a chance that confidentiality could be compromised; however, we take precautions to minimize this risk. As with all research, there is a chance that confidentiality could be compromised; however, we take precautions to minimize this risk.

1.4.3 Potential Benefits

If successful and reliable, the use of mass-produced consumer devices could be used in locations where traditional cardiopulmonary monitoring devices are unavailable. Alternatively, inaccurate device readings would have medicolegal implications of which patients, providers and healthcare systems should be aware. This information can help inform institutional policy.

1.5 Anticipated Duration of the Clinical Investigation

The overall duration of the study is estimated to be twelve months. 6 months recruitment and active study execution, 3 months analysis and 3 months for publication.

2 Study Objectives

2.1 Primary Objective

Measure the accuracy of wearable technology for patient monitoring compared to currently used equipment in patients undergoing gastrointestinal endoscopic procedures with sedation

2.2 Secondary Objective

1. Assess patient and provider preferences regarding wearable technology
2. Outline current practices and policies regarding wearable devices at Mayo Clinic

3 Study Design

3.1 General Design

We will perform a prospective, non-blinded, exploratory study to assess the accuracy and safety of smart technology in the endoscopy suite for patients undergoing gastrointestinal endoscopic procedures with sedation. We will also simultaneously perform an assessment of patient and provider preferences using narrative-driven, qualitative evaluation.

Patients will be identified by reviewing daily procedure listings on endoscopy units on Alfred 6, Gonda 2 and Gonda 9. Recruitment will occur over the phone the day prior to a procedure, or the pre-procedure areas on the day of the procedure. Patients who meet inclusion criteria and consent to participation in the study will be provided the smart devices. The devices will be secured to the wrist and torso by study personnel prior to administration of sedatives. The smart watch will be programmed to record respiratory rate, heart rate, and oximetry using native, first party device applications. These applications include *Blood Oxygen* (measures oxygen saturation), *ECG* (records single lead ECG), *Heart Rate* (heart rate), and *Health* (which logs respiratory rate while sleeping). The QardioCore ECG device will measure a single-lead ECG, heart rate, skin temperature, and respiratory rate.

The patient will undergo his or her scheduled procedure. Patients, proceduralists and anesthetists will not be blinded to their enrollment as the devices will be visible. On completion of the procedure, the devices will be removed by the study coordinator and data downloaded onto a central device for analysis. Procedural information will be extracted from the operative note, sedation record, and anesthesia encounter in EPIC. The day after the patient's procedure, a survey will be submitted to them electronically which will remain open until 14 days after

the procedure. Aen electronic reminder will be sent if uncompleted at 7 days, followed by a telephone reminder if not completed at 13 days. There will be no additional patient follow up after completion of the survey. At study completion, a survey will be sent to involved proceduralists and anesthetists.

3.2

Figure 1: Study Design

[figure not shown]

Table 1. Schedule of Events

	Baseline Screening & Enrollment Visit 1 Days -60 to 0	Accrual: Study Intervention Visit 2 Day 0	Patient Survey Visit 3 Day +1 to +14	Provider survey Days 0 to 180
Inclusion/ Exclusion	X	X (if not performed earlier)		
Device(s) Placement/ Recording		X		
Patient Survey			X	
Provider Survey				X

3.3 *Visit Descriptions*

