5.3 SUBJECT POPULATION(S) FOR ANALYSIS	12
6 SAFETY AND ADVERSE EVENTS	12
7 DATA HANDLING AND RECORD KEEPING	13
7.1 CONFIDENTIALITY.....	13
7.2 SOURCE DOCUMENTS.....	13
7.3 RECORDS RETENTION	14
8 STUDY MONITORING, AUDITING, AND INSPECTING	14
8.1 STUDY MONITORING PLAN	14
8.2 AUDITING AND INSPECTING	15
9 ETHICAL CONSIDERATIONS.....	15
10 STUDY FINANCES	15
10.1 FUNDING SOURCE	15
11 PUBLICATION PLAN	15

12	REFERENCES	15
13	ATTACHMENTS	ERROR! BOOKMARK NOT DEFINED.

LIST OF ABBREVIATIONS

CFR	Code of Federal Regulations
CRF	Case Report Form
DSMB	Data and Safety Monitoring Board
FDA	Food and Drug Administration
GCP	Good Clinical Practice
HIPAA	Health Insurance Portability and Accountability Act
IRB	Institutional Review Board
PHI	Protected Health Information
PI	Principal Investigator
SAE	Serious Adverse Event/Serious Adverse Experience
SOE	Schedule of Events
SOP	Standard Operating Procedure
IQR/M	Interquartile Range/Median

Study Summary

Title	A Prospective Study of the Role and Accuracy of Consumer-Facing Wearable Technology for Patient Monitoring in Gastrointestinal Endoscopy
Running Title	Wearable Technology Endoscopy
Title Acronym	Wearable Tech
IRB Protocol Number	21-007738
Phase	Prospective study
Methodology	Subjects who are eligible will have two consumer-facing wearable smart devices placed before scheduled endoscopy. Data from the devices will be downloaded after the procedure and analyzed. Patients and providers will complete a survey regarding their experience.
Overall Study Duration	6 months Recruitment and Active study execution, 3 months analysis and 3 months publication. Total: 12 months
Subject Participation Duration	Up to 60 days screening prior to study procedure, duration of the procedure itself, and completion of a survey within 14 days of procedure date
Objectives	Measure the accuracy and safety of wearable technology in patients undergoing endoscopic gastrointestinal procedures with sedation. Assess patient and provider preferences regarding wearable technology.
Number of Subjects	Five hundred (500)
Diagnosis and Main Inclusion Criteria	Subjects over 18 years of age who are scheduled to undergo an endoscopic procedure with sedation
Study Device	Consumer-facing wearable smart devices(examples include Apple Watch Series 6, FitBit Versa, The QardioCore ECG ambulatory monitoring device)
Reference Modality	Sedation/Anesthesia record

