3.3.2 Clinical Procedure/Accrual (Visit 2)

The devices will be secured to the wrist and torso by study staff prior to administration of sedatives. The devices will be programmed to record respiratory rate, heart rate, oximetry, skin temperature as well as single-lead ECG. The patient will undergo his or her scheduled procedure. On completion of the procedure, the devices will be removed by the study staff will download data onto a central device for analysis.

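### Section 5.2 limits the maximum/minimum comparison to the watch, omitting QardioCore heart rate and respiratory rate, and its whole-subject missing-data rule conflicts with 5.3

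*Combined protocol and SAP*

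**What the plan says.** The Study Summary states that subjects "will have two consumer-facing wearable smart devices placed before scheduled endoscopy", and section 3.1 has them secured to wrist and torso. For the wrist device, 3.1 says: "The smart watch will be programmed to record respiratory rate, heart rate, and oximetry using native, first party device applications". The one application it names for respiratory rate is Health, "which logs respiratory rate while sleeping". For the other device, 3.1 says: "The QardioCore ECG device will measure a single-lead ECG, heart rate, skin temperature, and respiratory rate". Section 3.3.2 repeats the intention for both together: "The devices will be programmed to record respiratory rate, heart rate, oximetry, skin temperature as well as single-lead ECG".

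Section 5.2 gives two accuracy measures. The first is an event concordance, defined as the number "of events recorded on wearable device / events noted on anesthesia record", which does not say which wearable. The second is to "calculate the difference in maximum and minimum heart rate, respiratory rate, and oxygen saturation recorded by the watch compared to the sedation record".

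On missing data, 5.2 keeps subjects with any missing or partial data out of the final analysis and reports what is available on them separately. Section 5.3 includes every subject who wore the device for the whole procedure. The primary objective in 2.1 concerns wearable technology in general, and 5.1 says that no statistical testing is planned.

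**The concern.** There are two gaps between what is collected and what is analysed.

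First, the objective covers wearable technology and two devices are worn, but the maximum/minimum comparison covers one. QardioCore heart rate and respiratory rate are to be measured, yet no section puts them into that comparison. Followed as written, the plan would give no such result for one of its two devices.

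Second, the missing-data rule acts on the whole subject. With three watch parameters, two devices and several applications, a gap in a single parameter is easy to imagine. Under 5.2 one gap moves everything else from that subject out of the main analysis; under 5.3 the subject stays in. The denominator for heart rate and oximetry would then depend on which section the analyst follows, and on whether an unrelated parameter was captured.

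In a descriptive study these summaries are the main result. What is at stake is which devices and which subjects they describe.

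**Working it through.** The plan gives no figure to reproduce on this point. The check is a tally of 3.1 against 5.2, followed by one subject traced through 5.2 and 5.3.

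**Step 1: inputs**
- Parameters in the maximum/minimum comparison (5.2): heart rate, respiratory rate, oxygen saturation.
- On the watch (3.1): all 3.
- On the QardioCore (3.1): heart rate and respiratory rate, so 2. Oximetry is not listed for it.
- Planned enrolment (Study Summary and section 4): 500.

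**Step 2: coverage of the maximum/minimum comparison**
- Device-parameter pairs: 3 + 2 = 5.
- Possible differences, a maximum and a minimum for each pair: 5 × 2 = 10.
- Planned in 5.2, watch only: 3 × 2 = 6.
- Omitted, QardioCore: 2 × 2 = 4, which is 4/10 of those possible.

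**Step 3: source device for the events**

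Section 5.2 lists five event types. Setting them against 3.1:
- Tachycardia and bradycardia need heart rate: both devices.
- Arrhythmia needs an ECG: both devices.
- Tachypnea needs respiratory rate: both devices.
- Desaturation needs oximetry: watch only.

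So 4 of 5 event types have two possible sources, and 5.2 does not say which one counts.

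**Step 4: one subject under the two rules**

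Take a subject who wore both devices throughout and has every value except watch respiratory rate.
- Section 5.3: included.
- Section 5.2, read literally: not in the final analysis, reported separately.
- Planned watch differences still available for this subject: 6 − 2 = 4 (heart rate and oximetry). With the QardioCore rows added: 10 − 2 = 8. Section 5.2 moves all of them.

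The same happens with any other single missing parameter.

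**Step 5: how many subjects**

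The documents give no capture rate for any parameter, so the share is unknown. Per 10 percentage points of enrolled subjects lacking one parameter: 500 × 0.10 = 50. This is a ceiling for three reasons. Section 5.3 covers only those who wore the device throughout. Section 4.4.2 bars further use of withdrawn subjects' data. Some of these subjects might also be incomplete for another reason.

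**The case against.** **Drafting shorthand.** The reference to the watch in 5.2 may be loose wording. Section 1.2 adds the QardioCore as an accessory after a repeated paragraph on smart watches, section 1.4.2 still speaks of placing a watch, and the Study Summary names devices only by way of illustration ("examples include Apple Watch Series 6, FitBit Versa, The QardioCore ECG ambulatory monitoring device"). This is plausible, and nothing bars the sponsor from adding descriptive rows. But 3.1 treats the smart watch and the QardioCore as different devices with different measurements, so 5.2 as written does not cover the second. That this may be a wording fault lowers the severity; it does not remove the point.

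**The QardioCore is still analysed.** A reader might infer that it is left out of the accuracy analysis altogether. The documents do not support that: the concordance refers to a wearable device without restriction and can include it. The omission is confined to the maximum/minimum comparison.

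**Watch respiratory rate will be missing.** A reader might infer this from the sleep log. It is not shown. Sections 3.1 and 3.3.2 say respiratory rate will be recorded, 1.2 credits smart watches with measuring it without a sleep condition, the application list in 3.1 is not presented as complete, and no section says whether the application logs under sedation. It is a question for the sponsor.

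**The two population rules can be read in sequence.** Section 5.3 could define who qualifies by wear, and 5.2 could then remove incomplete records. That reading is possible, but 5.3 says all such subjects are analysed, and even in sequence the rule discards usable parameters from the main analysis. Nor are the data lost, because 5.2 reports them separately. That limits the harm.

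**The study is descriptive.** This stands. No test or stated precision is affected.

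**Conclusion.** The point holds, at minor severity. Followed as written, 5.2 omits 4 of 10 possible maximum/minimum differences, all from the QardioCore, from a measure that serves the primary objective. That count follows directly from 3.1 and 5.2 and rests on no assumption beyond taking the watch and the QardioCore as the two devices worn.

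The missing-data rule in 5.2 and the population in 5.3 give different answers for a subject who wore the devices throughout but lacks one parameter. The number of such subjects cannot be derived from the documents, and any figure scaled on 500 overstates it. The effect is on what is reported and for whom; no hypothesis test is at risk.

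**What to change.** Two changes to 5.2:

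1. Add QardioCore heart rate and respiratory rate to the maximum/minimum comparison, report each device separately, and state which device supplies each event type in the concordance.
2. Apply the missing-data rule per parameter and device, in line with 5.3, so that an absent value removes only its own comparison. Report the number of subjects with any value for each parameter and device. That count will also answer the query about watch respiratory rate.

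Both are text changes and use data the study already plans to collect. The cost is a little more analysis and a different denominator for each parameter and device, which the tables must show. Settling this before the data are analysed also avoids choosing devices or denominators after seeing the results.
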